8.2 End of Study Definition

The start of the study is defined as the first visit for first subject screening. The end of the study is defined as the last visit or scheduled procedure shown in the Schedule of Activities (Section 1) for the last subject. Subjects who withdraw early from the study will be requested to complete the study discharge evaluations.

8.3 Study Population

Eligibility criteria for this study have been carefully considered to ensure the safety of the study subjects. It is imperative that subjects fully meet all eligibility criteria as all arms of the study will be conducted under a "no-waiver" policy.

All screening evaluations must be completed and reviewed to confirm that potential subjects meet all eligibility criteria. The Investigator will maintain a screening log to record details of all subjects screened and to confirm eligibility or record reasons for screening failure, as applicable.

To be eligible for the study, subjects must meet the criteria in Sections [8.3.1](#) and [8.3.2](#).

8.3.1 Inclusion Criteria

8.3.1.1 Healthy Subjects (Part A and B)

1. Subjects must be willing and able to participate in the study, sign the ICF, and complete all study-specific procedures and visits.
2. Males and females, ages 18 to 55 years, inclusive, at screening.
3. Healthy subjects, as determined by no clinically significant deviations from normal in medical history, physical examination, 12-lead ECGs, vital signs, and clinical laboratory results.
4. Body mass index (BMI) of 18.0 to 30.0 kg/m², inclusive, at screening.
BMI = weight (kg)/height (m)².
5. Body weight between 55 and 105 kg, inclusive, at screening.
6. Females that meet one of the following:
 - a. Women of childbearing potential (WOCBP) must have a negative serum or urine pregnancy test at screening and prior to the start of investigational product (IP) and must agree to follow instructions for method(s) of contraception ([Appendix 3](#)) for the duration of the study and a minimum of 3 months after dosing has been completed.
 - b. Premenopausal female with 1 of the following:
 - i. Documented hysterectomy
 - ii. Documented bilateral salpingectomy
 - iii. Documented bilateral oophorectomy
 - iv. Sexual abstinence as preferred or usual lifestyle of the subject.
 - c. Postmenopausal women (12 months or more amenorrhea and over 45 years of age in the absence of other biological or physiological causes). Females under 55 years of age require follicle stimulating hormone (FSH) >40 mIU/mL at screening
7. Women must not be breastfeeding.
8. Males that meet one of the following:
 - a. Males who are sexually active with WOCBP must agree to follow instructions for method(s) of contraception ([Appendix 3](#)) for the duration of the study and a minimum of 3 months after dosing has been completed. In addition, male subjects must be willing to refrain from sperm donation during this time.
 - b. Vasectomized males are exempt from contraceptive requirements.

Investigators shall counsel WOCBP, and male subjects who are sexually active with WOCBP, on the importance of pregnancy prevention and the implications of an unexpected pregnancy.

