APPENDIX 3 WOMEN OF CHILDBEARING POTENTIAL DEFINITIONS AND METHODS OF CONTRACEPTION

DEFINITIONS

Woman of Childbearing Potential (WOCBP)

A woman is considered fertile following menarche and until becoming postmenopausal unless permanently sterile. Permanent sterilization methods include hysterectomy, bilateral salpingectomy, and bilateral oophorectomy.

Women in the following categories are not considered WOCBP:

- Premenarchal
- Premenopausal female with 1 of the following:
 - Documented hysterectomy
 - Documented bilateral salpingectomy
 - Documented bilateral oophorectomy

Note: Documentation can come from the site personnel's review of the participant's medical records, medical examination, or medical history interview.

Postmenopausal female

A postmenopausal state is defined as 12 months of amenorrhea in a woman over age 45 years in the absence of other biological or physiological causes. In addition, females under the age of 55 years must have a serum follicle stimulating hormone (FSH) level > 40 mIU/mL to confirm menopause.

Note: Females treated with hormone replacement therapy (HRT) are likely to have artificially suppressed FSH levels and may require a washout period in order to obtain a physiologic FSH level. The duration of the washout period is a function of the type of HRT used. The duration of the washout periods below are suggested guidelines and the investigators should use their judgment in checking serum FSH levels.

- 1 week minimum for vaginal hormonal products (rings, creams, gels)
- 4 week minimum for transdermal products
- 8 week minimum for oral products

Other parenteral products may require washout periods as long as 6 months. If the serum FSH level is > 40 mIU/mL at any time during the washout period, the woman can be considered postmenopausal.

CONTRACEPTION GUIDANCE FOR FEMALE PARTICIPANTS OF CHILD BEARING POTENTIAL

One of the methods of contraception listed below is required for the duration of treatment with BMS-986251 until at least 3 months post treatment completion.

- Non-hormonal intrauterine device
- Intrauterine hormone-releasing system
- Bilateral tubal occlusion
- Complete abstinence as defined below
- Vasectomized partner with documented azoospermia 3 months after procedure

Local laws and regulations may require use of alternative and/or additional contraception methods.

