
• Sexual abstinence: Sexual abstinence is considered a highly effective method only if defined as refraining from heterosexual intercourse during the entire period of risk associated with the study drug. The reliability of sexual abstinence needs to be evaluated in relation to the duration of the study and the preferred and usual lifestyle of the participant.
○ It is not necessary to use any other method of contraception when complete abstinence is elected.○ WOCBP participants who choose complete abstinence must continue to have pregnancy tests, as specified in Section 1.○ Acceptable alternate methods of highly effective contraception must be discussed in the event that the WOCBP participants chooses to forego complete abstinence○ The reliability of sexual abstinence needs to be evaluated in relation to the duration of the clinical trial and the preferred and usual lifestyle of the subject
Less Than Highly Effective Contraceptive Methods That Are User Dependent

• Male or female condom with or without spermicide. Male and female condoms cannot be used simultaneously• Diaphragm with spermicide• Cervical cap with spermicide• Vaginal sponge with spermicide• Progestogen-only oral hormonal contraception, where inhibition of ovulation is not the primary mechanism of action
Unacceptable Methods of Contraception

• Periodic abstinence (calendar, symptothermal, postovulation methods)• Withdrawal (coitus interruptus).• Spermicide only• Lactation amenorrhea method

CONTRACEPTION GUIDANCE FOR MALE PARTICIPANTS WITH PARTNER(S) OF CHILD BEARING POTENTIAL

Male participants with female partners of childbearing potential are eligible to participate if they agree to the following during the treatment and until the end of relevant systemic exposure.

- Inform any and all partner(s) of their participation in a clinical drug study and the need to comply with contraception instructions as directed by the investigator.
- Male participants are required to use a condom for study duration and a minimum of 3 months after dosing has been completed.

- Female partners of males participating in the study to consider use of effective methods of contraception for the duration of the study and a minimum of 3 months after dosing has been completed.

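### Inclusion 6b(iv) and 8b(iv) place sexual abstinence beside surgical sterility, so an abstinent fertile woman can qualify without the explicit pregnancy-test and contraception conditions, although Appendix 3 treats her as a woman of childbearing potential (low severity).

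*Protocol*

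**What the plan says.** Inclusion 6 (Protocol 8.3.1.1) opens with "Females that meet one of the following" and gives three branches. Inclusion 8 (Protocol 8.3.1.2, Part C) has the same structure and wording.

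- **Branch a** covers WOCBP. It requires a negative pregnancy test at screening and before the first dose, and agreement to the Appendix 3 contraception instructions for the study and at least 3 months after dosing.
- **Branch b** covers premenopausal women with one of four items: documented hysterectomy, documented bilateral salpingectomy, documented bilateral oophorectomy, or "Sexual abstinence as preferred or usual lifestyle of the subject". It sets no test result and no commitment after dosing.
- **Branch c** covers postmenopausal women.

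Appendix 3 introduces its exempt groups with "Women in the following categories are not considered WOCBP". Its premenopausal entry there has the three operations and nothing else. Abstinence appears under contraception for participants of childbearing potential, as "Complete abstinence as defined below", among methods of which one "is required for the duration of treatment with BMS-986251 until at least 3 months post treatment completion". Appendix 3 accepts abstinence only when it covers the whole period of risk from the study drug, and adds: "WOCBP participants who choose complete abstinence must continue to have pregnancy tests, as specified in Section 1".

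Protocol 8.3 sets a no-waiver policy: "It is imperative that subjects fully meet all eligibility criteria".

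**The concern.** The same woman is classified in two ways. In Appendix 3, a fertile woman who abstains is a WOCBP with a contraceptive method. In the inclusion criterion she sits in a list that otherwise holds only surgically sterile women, and that list carries no pregnancy or contraception condition. Because one branch is enough, she can qualify on item iv alone.

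The standard of abstinence also differs. Item iv asks about preferred or usual lifestyle, which describes current habit. Appendix 3 asks for a commitment through the risk period.

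At stake is a pregnancy-safety rule in a first-in-human trial that allows no waivers. Under such a policy the written criterion decides entry, so it should agree with the protocol's own definition of WOCBP.

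**Working it through.** There is no plan figure to reproduce. The check is a comparison of texts, followed by a look at what else in the protocol would catch the case.

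**Step 1. The three texts side by side, for a fertile premenopausal woman who abstains**

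| Point | Inclusion 6a / 8a | Inclusion 6b(iv) / 8b(iv) | Appendix 3 |
|---|---|---|---|
| Status | WOCBP | Listed with the surgically sterile | WOCBP (neither postmenopausal nor permanently sterile) |
| Negative test at screening and before dosing as a stated criterion | Yes | No | Not an entry text; says testing continues |
| Agreement to at least 3 months after dosing as a stated criterion | Yes | No | Method required until at least 3 months after treatment |
| Standard for abstinence | By reference to Appendix 3 | Preferred or usual lifestyle | Entire risk period |

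**Step 2. Where the lists differ.** Branch b has 4 premenopausal items and the Appendix 3 list of women who are not WOCBP has 3. The difference, 4 − 3 = 1, is abstinence.

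**Step 3. The logic of entry.** She satisfies b(iv). The opening words of the criterion require only one branch. She therefore meets inclusion 6 or 8 without meeting branch a. Neither exclusion list (8.3.2.1, 8.3.2.2) names pregnancy or a positive pregnancy test, so branch a is the only criterion that expressly asks for a negative result.

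**Step 4. What else would catch her**

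- *Testing.* Tables 1 to 4 schedule a pregnancy test for all females at screening, pre-treatment and follow-up. Section 8.5.2.4 requires Day -1 laboratory results to be in hand before first dosing. In the Part C sparse sub-cohort the pre-treatment test falls on Day 1 instead (Table 4).
- *A positive result.* Table 10 lists the pregnancy test among the clinical laboratory assessments. Inclusion 3 (Parts A and B) and inclusion 7 (Part C) bar clinically significant laboratory abnormalities, with an allowance in Part C for those expected in psoriasis patients. An investigator could exclude a positive test on that ground, as a matter of judgement.
- *Contraception.* Appendix 3 duties follow from WOCBP status, whichever branch she entered by. Exclusion 30 (Parts A and B) and exclusion 38 (Part C) bar anyone unable to comply with protocol restrictions. Sections 8.3.1.1, 8.3.1.2 and 8.5.2.1.5 require counselling of WOCBP.

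**Step 5. How many subjects it could touch.** SAP 7.1 gives the numbers dosed: Part A 8 + 8 + 8 + 8 + 4 = 36, Part B 2, total 36 + 2 = 38. These are both sexes, active and placebo. Part C was not executed (SAP 6.0), so 8b(iv) applied to nobody dosed. Among dosed subjects, 6b(iv) could have applied only to abstinent fertile women among the 38. The documents give no count of them.

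**The case against.** The best defence is that branch a states a duty of WOCBP in mandatory terms, and Appendix 3 makes the abstinent fertile woman a WOCBP, so the duty reaches her however she enters. Branch b never says that its members are not WOCBP, and item iv echoes the lifestyle wording that Appendix 3 uses for abstinence. It can be read as a pointer to that method. The no-waiver policy forbids exceptions; it does not favour the most permissive branch.

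This is a fair reading, but it does not save item iv. If branch a binds her anyway, item iv does nothing. If it does not, item iv waives the conditions. Deletion is right in both cases. The male criterion next to it has the same shape, with a duty in a and an express exemption in b for vasectomised men, so a reader could easily take female branch b as an exemption too.

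The defence does succeed on size. A reader might infer that fertile women could be dosed untested, that a pregnant woman could not be kept out, or that no contraception duty applied. The documents support none of these: all females are tested, the general laboratory criterion gives the investigator a ground to exclude a positive result, and Appendix 3 applies by WOCBP status. Nor does either document show that any woman entered through b(iv) or came to harm.

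**Conclusion.** The conflict between 6b(iv)/8b(iv) and Appendix 3 is real, and the criteria as written are wrong on this line. What is lost for an abstinent fertile woman is narrow: the explicit criterion that her pregnancy tests be negative, and her explicit agreement in advance to cover the period to at least 3 months after dosing. Testing itself and the contraception duty remain.

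Severity is low. No endpoint, analysis or study procedure changes. The conclusion rests on a literal reading of the opening words of the criterion, and on treating the route through inclusion 3 or 7 as general and discretionary, not as a stated pregnancy criterion. Since the study was terminated, the practical value lies in any restart or reuse of this eligibility text.

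**What to change.** Delete item iv from inclusion 6b and from inclusion 8b. Abstinent fertile women then enter through 6a or 8a, with complete abstinence as their Appendix 3 method, negative tests at screening and before dosing, and agreement until at least 3 months after dosing.

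The cost is one line removed from each of two criteria. No procedure is added, because all females are already tested. A woman who will maintain abstinence, as Appendix 3 already requires, still qualifies.

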8.3.1.2 Psoriasis Patients (Part C)

1. Subjects must be willing and able to participate in the study and sign the ICF, and be willing and able to complete all study-specific procedures and visits.
2. Males and females, ages 18 to 70 years, inclusive, at screening.
3. BMI of 18.0 to 35.0 kg/m², inclusive, at screening. BMI = weight (kg)/height m².
4. Body weight between 55 and 120 kg, inclusive, at screening.

5. Diagnosed with stable chronic plaque psoriasis, for at least 6 months prior to screening and be candidates for either photo-therapy or systemic treatment.
6. Moderate-to-severe intensity of psoriasis as defined by:
 - a. Affected body surface area (BSA) of $\geq 10\%$.
 - b. Psoriasis Area and Severity Index (PASI) ≥ 12 .
 - c. Physician Global Assessment (PGA; 6-point scale) ≥ 3 .
7. No clinically significant deviations from normal in medical history, physical examination, 12-lead ECGs, vital signs, and clinical laboratory results, other than abnormalities expected for this patient population, as judged by the Investigator.
8. Females that meet one of the following:
 - a. WOCBP must have a negative serum or urine pregnancy test at screening and prior to the start of IP and must agree to follow instructions for method(s) of contraception ([Appendix 3](#)) for the duration of the study and a minimum of 3 months after dosing has been completed.
 - b. Premenopausal female with 1 of the following:
 - i. Documented hysterectomy.
 - ii. Documented bilateral salpingectomy.
 - iii. Documented bilateral oophorectomy.
 - iv. Sexual abstinence as preferred or usual lifestyle of the subject.
 - c. Postmenopausal women (12 months or more amenorrhea and over 45 years of age in the absence of other biological or physiological causes). Females under 55 years of age require FSH >40 mIU/mL at screening
9. Women must not be breastfeeding.
10. Males that meet one of the following:
 - a. Males who are sexually active with WOCBP must agree to follow instructions for method(s) of contraception ([Appendix 3](#)) for the duration of the study and a minimum of 3 months after dosing has been completed. In addition, male subjects must be willing to refrain from sperm donation during this time.
 - b. Vasectomized males are exempt from contraceptive requirements.

Investigators shall counsel WOCBP, and male subjects who are sexually active with WOCBP, on the importance of pregnancy prevention and the implications of an unexpected pregnancy.

8.3.2 Exclusion Criteria

8.3.2.1 Healthy Subjects (Part A and B)

1. Previous participation in the current study.
2. Participation in a drug study or exposure to any investigational drug or placebo within 2 months prior to (the first) drug administration in the current study. Participation in more than 4 other drug studies in the 12 months prior to (the first) drug administration in the current study.
3. Employees of PRA or the Sponsor and their relatives.
4. Any significant acute or chronic medical condition that presents a potential risk to the subject and/or that may compromise the objectives of the study, including active, or history of, liver disease, or intestinal disorder including irritable bowel syndrome.

5. Current or recent (within 3 months of study treatment administration) gastrointestinal disease that could affect pharmacokinetics; history of cholecystectomy is not allowed.
6. Major surgery within 4 weeks of (first) study treatment administration.
7. History or presence of malignancy including hematological malignancies; subjects with a history of basal cell or squamous cell carcinoma that has been treated with no evidence of recurrence will be allowed for inclusion, as judged by the Investigator.
8. Documented congenital QT syndrome, and/or corrected QT interval (Fridericia correction) at screening or first admission >450 ms.
9. Donation or loss of more than 100 mL of blood within 2 months prior to (the first) drug administration. Donation or loss of more than 1.5 L of blood (for male subjects)/more than 1.0 L of blood (for female subjects) in the 10 months prior to (the first) drug administration in the current study.
10. Inability to be venipunctured and/or tolerate venous access.
11. Subjects who have smoked or used smoking cessation or nicotine containing products (including, but not limited, to e-cigarettes, pipes, cigars, chewing tobacco, nicotine patches, nicotine lozenges, or nicotine gum, varenicline, bupropion) within 6 months of the first dose of study drug.
12. Abuse or drug addiction (including cannabis products) within one year before screening ([Appendix 4](#)).
13. Average intake of more than 24 units of alcohol per week (1 unit of alcohol equals approximately 250 mL of beer, 100 mL of wine or 35 mL of spirits).
14. Positive drug and alcohol screen (opiates, methadone, cocaine, amphetamines [including ecstasy], cannabinoids, barbiturates, benzodiazepines, tricyclic antidepressants and alcohol) at screening or admission to the CRU.
15. Consumption of caffeine or xanthine-containing food or beverages from at least 72 hours prior to admission to the CRU until at least 24 hours after last drug administration.
16. Consumption of any nutrients known to modulate CYP enzymes activity (eg, grapefruit or grapefruit juice, pomelo juice, star fruit, or Seville [blood] orange products) within 14 days prior to first administration of study drug until after discharge in the last treatment period.
17. Positive blood screen for hepatitis C antibody, hepatitis B surface antigen (HBsAg), or HIV-1 or -2 antibodies.
18. History of any significant drug and/or food allergies (such as anaphylaxis or hepatotoxicity).
19. Use of any prescription drugs within 4 weeks prior to study drug administration except those medications cleared by the Investigator and PRA Medical Monitor.
20. Use of over-counter (OTC) medications and herbal preparations within 2 weeks prior to study drug administration, except those medications cleared by the Investigator and PRA Medical Monitor.
21. Any history or risk for tuberculosis (TB), specifically subjects with: 1) current clinical, radiographic or laboratory evidence of active TB; 2) history of active TB; 3) positive Quantiferon[®] test result and history of latent TB, unless subject has documentation of completion of anti-TB treatment.

22. Known or suspected autoimmune disorder, or any history of known or suspected congenital or acquired immunodeficiency state or condition that would compromise the subject's immune status (eg, history of splenectomy).
23. Presence of any factors that would predispose the subject to develop infection eg, bronchial asthma, rectal fissures, poor dentition, open skin lesions, and presence of pre-existing skin conditions eg, Behcet's Disease, psoriasis, pustular dermatoses.
24. Any serious (eg, requiring intramuscular or IV antibiotics and/or hospitalization) acute or chronic bacterial, viral or fungal infection (eg, pneumonia, septicemia) within the 3 months prior to screening.
25. Active herpes infection, including herpes simplex 1 and 2 and herpes zoster within 2 months of administration of study medication.
26. History of malaria.
27. History or any evidence of active infection or febrile illness within 7 days of dosing (eg, bronchopulmonary, urinary, or gastrointestinal).
28. History of recurrent or chronic sinusitis, bronchitis, pneumonia, urinary tract infection (recurrent or chronic urinary tract infection is 2 episodes within 6 months).
29. Immunization with live vaccines or live-attenuated within 2 months prior to Day 1.
30. Inability to comply with protocol procedures, assessments, restrictions, and prohibited treatments.
31. Legal incapacity or limited legal capacity.

8.3.2.2 Psoriasis Patients (Part C)

1. Previous participation in the current study.
2. Participation in a drug study or exposure to any investigational drug or placebo within 2 months prior to (the first) drug administration in the current study.
3. Employees of PRA or the Sponsor and their relatives.
4. Any significant acute or chronic medical condition that presents a potential risk to the subject and/or that may compromise the objectives of the study, including active, or history of, liver disease, or intestinal disorder including irritable bowel syndrome.
5. Current or recent (within 3 months of study treatment administration) gastrointestinal disease that could affect pharmacokinetics; history of cholecystectomy is not allowed.
6. Major surgery within 4 weeks of (first) study treatment administration.
7. History or presence of malignancy including hematological malignancies; subjects with a history of basal cell or squamous cell carcinoma that has been treated with no evidence of recurrence will be allowed for inclusion, as judged by the Investigator.
8. Documented congenital QT syndrome, and/or corrected QT interval (Fridericia correction) at screening or first admission >450 ms.
9. Uncontrolled treated/untreated hypertension (defined as a mean of 3 repeated measurements for systolic blood pressure ≥ 160 mmHg and/or diastolic blood pressure ≥ 105 mmHg); current or documented history of repeated clinically significant hypotension or severe episodes of orthostatic hypotension (systolic blood pressure < 90 mmHg and/or diastolic blood pressure < 50 mmHg).
10. Evidence of organ dysfunction or any clinically significant deviation from normal in physical examination, vital signs, ECG, or clinical laboratory results beyond what is consistent with the target population, including any of the following laboratory exclusion criteria:

- a. Leukopenia defined as absolute WBC count $< 3000/\text{mm}^3$ within 28 days of dosing with study drug on Day 1
- b. Lymphopenia defined as absolute lymphocyte count $< 500/\text{mm}^3$ within 28 days of dosing with study drug on Day 1
- c. Neutropenia defined as absolute neutrophil count $< 1000/\text{mm}^3$ within 28 days of dosing with study drug on Day 1
- d. Moderate to severe thrombocytopenia defined as platelet count $< 100,000/\text{mm}^3$ within 28 days of dosing with study drug on Day 1
- e. Moderate to severe anemia defined as hemoglobin < 9 g/dL within 28 days of dosing with study drug on Day 1
- f. ALT and/or AST $> 3X$ ULN within 28 days of dosing with study drug on Day 1
- g. Total, unconjugated, and/or conjugated bilirubin $> 2X$ ULN within 28 days of dosing with study drug on Day 1
11. Donation or loss of more than 100 mL of blood within 2 months prior to (the first) drug administration. Donation or loss of more than 1.5 L of blood (for male subjects)/more than 1.0 L of blood (for female subjects) in the 10 months prior to (the first) drug administration in the current study.
12. Inability to be venipunctured and/or tolerate venous access.
13. Subjects who have smoked or used smoking cessation or nicotine containing products (including, but not limited, to e-cigarettes, pipes, cigars, chewing tobacco, nicotine patches, nicotine lozenges, or nicotine gum, varenicline, bupropion) within 6 months of the first dose of study drug.
14. Abuse or drug addiction (including cannabis products) within one year before screening ([Appendix 4](#)).
15. Average intake of more than 24 units of alcohol per week (1 unit of alcohol equals approximately 250 mL of beer, 100 mL of wine or 35 mL of spirits).
16. Positive drug and alcohol screen (opiates, methadone, cocaine, amphetamines [including ecstasy], cannabinoids, barbiturates, benzodiazepines [if not prescribed or otherwise medically indicated, eg for anxiety, insomnia etc., and properly documented in concomitant medication], and alcohol) at screening or admission to the CRU.
17. Consumption of caffeine or xanthine-containing food or beverages from at least 72 hours prior to admission to the CRU and during the stays at the CRU.
18. Consumption of any nutrients known to modulate CYP enzymes activity (eg, grapefruit or grapefruit juice, pomelo juice, star fruit, or Seville [blood] orange products) within 14 days prior to first administration of study drug until after discharge in the last treatment period.
19. Subjects diagnosed with erythrodermic psoriasis, pustular psoriasis, guttate psoriasis, medication-induced psoriasis, or other skin conditions at the time of the screening visit (eg, eczema) that would interfere with evaluations of the effect of IP on psoriasis.
20. Treatment with experimental or commercially available biological agents such as, but not limited to, etanercept, adalimumab, infliximab, certolizumab pegol within 3 months prior to Day 1.
21. Systemic immunosuppressants (such as, but not limited to, methotrexate, cyclosporine A, mycophenolate, tacrolimus, azathioprine, 6-thioguanine, mercaptopurine

- and hydroxyurea), corticosteroids, or phototherapy (UV A light therapy [with or without psoralen], UV B light therapy, or excimer laser) within 1 month prior to Day 1.
22. Topical corticosteroid treatment other than low-strength or lower-mid strength corticosteroids on the face, scalp, axillae, and/or groin within 2 weeks prior to Day 1.
 23. Concomitant medications (prescription, OTC, or herbal) outside the stable standard of care regimens for psoriasis administered during the study unless prescribed by the Investigator for treatment of specific clinical events.
 24. Positive blood screen for hepatitis C antibody, HBsAg, or HIV-1 or -2 antibodies.
 25. History of any significant drug and/or food allergies (such as anaphylaxis or hepatotoxicity).
 26. Use of any prescription drugs within 4 weeks prior to study drug administration except those medications cleared by the Investigator and PRA Medical Monitor.
 27. Use of OTC medications and herbal preparations within 2 weeks prior to study drug administration, except those medications cleared by the Investigator and PRA Medical Monitor.
 28. Concomitant medications that are strong inhibitors or inducers of CYP3A4 or transporters administered within 2 weeks or 5 half-lives, whichever is longer, prior to the start of the study and throughout the study. Patients on stable standard of care medications that are moderate inhibitors or inducers of CYP3A4 or transporters will be cleared for use by the Investigator and PRA Medical Monitor. For guidance, please refer to <http://medicine.iupui.edu/clinpharm/ddis/clinical-table> or <https://www.fda.gov/drugs/developmentapprovalprocess/developmentresources/druginteractionslabeling/ucm093664.htm>
 29. Any history or risk for TB, specifically subjects with: 1) current clinical, radiographic or laboratory evidence of active TB; 2) history of active TB; 3) positive Quantiferon[®] test result and history of latent TB, unless subject has documentation of completion of anti-TB treatment.
 30. Known or suspected autoimmune disorder, except psoriasis, or any history of known or suspected congenital or acquired immunodeficiency state or condition that would compromise the subject's immune status (eg, history of splenectomy or diabetes).
 31. Presence of any factors that would predispose the subject to develop infection eg, bronchial asthma, rectal fissures, poor dentition.
 32. Any serious (eg, requiring intramuscular or IV antibiotics and/or hospitalization) acute or chronic bacterial, viral, or fungal infection (eg, pneumonia, septicemia) within the 3 months prior to screening.
 33. Active herpes infection, including herpes simplex 1 and 2 and herpes zoster within 2 months of administration of study medication.
 34. History of malaria.
 35. History or any evidence of active infection or febrile illness within 14 days of dosing (eg, bronchopulmonary, urinary, or gastrointestinal).
 36. History of recurrent or chronic sinusitis, bronchitis, pneumonia, urinary tract infection (recurrent or chronic urinary tract infection is 2 episodes within 6 months).
 37. Immunization with live vaccines or live-attenuated within 2 months prior to Day 1.
 38. Inability to comply with protocol procedures, assessments, restrictions, and prohibited treatments.
 39. Legal incapacity or limited legal capacity.

